4.2. Labeling

This study is open-labeled; therefore, the patient, the investigator's site personnel, supporting company representative, and the MDACC IND Office or its designee are not blinded to study treatment. Each vial of IP will be labeled with a single panel label.

Labels will be prepared in accordance with Good Manufacturing Practice and local regulatory guidelines. The labels will fulfill Good Manufacturing Practice Annex 13 requirements for labeling. Label text will be translated into local language.

Example labels for the CELLECTRA®5P Device (Pulse Generator, Applicator and Array) are shown in Figure 2.

Version Number: 1.8 Date: July 26, 2019

Proprietary of MD Anderson Cancer Center

[figure not shown]

Figure 2. Examples of labeling for the CELLECTRA®5P

4.3. Study Drug Preparation

It is the responsibility of the investigator to ensure that IP is dispensed to study participants. It must be dispensed only from official study sites by authorized personnel according to local regulations and must be recorded appropriately on the IP accountability record.

4.3.1. MEDI0457

Vial contents must be thawed at ambient room temperature and must be administered within 4 hours of removal from freezer.

The study personnel will draw 1 mL of MEDI0457 from the pre-filled vials using a syringe. This syringe will be used to administer IP to the patients IM through the CELLECTRA®5P device.

Version Number: 1.8 Date: July 26, 2019

Proprietary of MD Anderson Cancer Center

The syringe must be labeled with the date and time it was removed from the freezer and a 4-hour expiration date and time from the time the vial is removed from the freezer. The label should also contain the words "administer as soon as possible".

4.3.2. Durvalumab

All doses will be prepared in infusion bags under aseptic conditions by trained personnel; it should not be prepared on the ward. No incompatibilities between Durvalumab and polyvinylchloride or polyolefin IV bags have been observed.

Durvalumab will be administered using an IV bag containing 0.9% (w/v) saline, with a final Durvalumab concentration ranging from 1 to 20 mg/mL, and delivered through an IV administration set with a 0.2- or 0.22- μ m in-line filter.

For patients ≥30 kg, remove 30.0 mL of IV solution from the IV bag prior to addition of Durvalumab. Next, 30.0 mL of Durvalumab (i.e., 1500 mg of Durvalumab) is added to the IV bag such that final concentration is within 1 to 20 mg/mL (IV bag volumes 100 to 1000 mL). Mix the bag by gently inverting to ensure homogeneity of the dose in the bag.

For patients < 30 kg, calculate the dose volume of Durvalumab and number of vials needed for the subject to achieve the accurate dose according to **Appendix F**.

4.4. Doses and Treatments

4.4.1. Planned Dosing Schedule

All patients will receive combination treatment with MEDI0457 and durvalumab as per the following **Planned Dosing Schedule** (treatment should be given at the beginning of the week, unless otherwise specified) as detailed in **Figure 1** and **Table 3**.

Durvalumab will be administered at a fixed dose of 1500 mg q4wk for patients that are \ge 30 kg. For patients who weigh <30 kg, weight-based dosing will be used at a dose of 20 mg/kg q 4 weeks, and if their weight increases to \ge 30 kg they can be switched to durvalumab at 1500 mg every 4 weeks.

Patients will receive 7 mg MEDI0457 delivered by IM followed by EP on Day 1 (Week 1), Week 3, Week 7, Week 12 and then every 8 weeks until disease progression or unacceptable toxicity. Durvalumab will be administered on Week 4, Week 8, Week 12 and then every 4 weeks until disease progression or unacceptable toxicity. On days when both MEDI0457 and durvalumab administrations will occur on the same day (Week 12 then every 8 weeks), MEDI0457 will be administered first, and durvalumab IV infusion will start approximately 1 hour after MEDI0457 is delivered intramuscularly followed by EP.

Minimum time between Week 3 MEDI0457 dose and the Week 4 first durvalumab dose, and the Week 7 MEDI0457 dose and the Week 8 durvalumab dose is 7 days.

Version Number: 1.8 Proprietary of MD Anderson Cancer Center Page 1019 26 2019

4.4.2. **Durvalumab**

Durvalumab will be administered at a fixed dose of 1500 mg q4w in the combination and monotherapy arms for patients weighing \geq 30 kg. For patients weighing \leq 30 kg, the dose will be 20 mg/kg. The maximum number of doses of checkpoint inhibitor therapy will equal 13.

The duration will be approximately 1 hour (± 5 minutes) for each durvalumab infusion. A 1- hour observation period is required after the first infusion of durvalumab is administered. If no clinically significant infusion reactions are observed during or after the first dose, subsequent infusion observation periods can be at the investigator's discretion (suggested 30 minutes after each durvalumab infusion).

Patients will be monitored during and after the infusion with assessment of vital signs at the times specified in the study protocol.

See Section 6.7.1 dose administration changes in the event of Grade 1 or 2 infusion-related reactions.

4.4.3. **MEDI0457**

The DNA vaccine is administered in two steps. In step 1 the vaccine is injected intramuscularly through the CELLECTRA®5P device. Step 2 follows immediately as the CELLECTRA®5P device delivers a sequence of electroporation pulses to the injection area.

Patients will be offered topical anesthetic (e.g., EMLA [lidocaine + prilocaine]), to prevent significant discomfort from the study treatment procedure. If EMLA (lidocaine 2.5% and prilocaine 2.5%) is used, an approximately 1.5 cm diameter amount will be applied with occlusion to the site of injection ~30 minutes prior to study treatment.

Patients may be offered a mild sedative (e.g., 0.5-1 mg lorazepam) for anxiety related to the EP procedure. Mild sedatives may be administered approximately 1 hour prior to EP. Patients who receive a mild sedative must not be allowed to operate a motor vehicle for 3-4 hours after receiving medication and must have arranged transportation to depart the study site.

Patients will be offered an analgesic (e.g., ibuprofen, ketorolac) after study treatment. The use of any narcotic (including Tylenol® [acetaminophen] with codeine) for pain meets the definition of severe pain (Grade 3) and therefore will not be offered to the patients unless clinically indicated.

Patients who are allergic to or have contraindications to ibuprofen, ketorolac or lorazepam will be offered a suitable alternative.

Medications administered to manage anxiety and pain due to the EP procedure will be captured as concomitant medications in the database.

The instructions for use of the CELLECTRA®5P device are located in the Operations Manual. Each clinical site will receive training for the use of the CELLECTRA®5P device. The following specifications will be used during the study:

Version Number: 1.8
Date: July 26, 2019

Proprietary of MD Anderson Cancer Center

- Number of pulses=3
- Current Strength=0.5 Amp
- Electroporation pulse duration=52 milliseconds/pulse
- Interval separating pulses=1 second

The injection/EP procedure must be performed by qualified personnel. Any individual designated to perform the procedure should be permitted by the relevant local authorities to administer parenteral medications to patients in addition to receiving device training from Inovio personnel. Individuals whose credentials do not meet the relevant local requirements may perform the injection/EP procedure under the conditions below:

- The procedure must be performed under the direct supervision of the Principal Investigator or an approved Sub-Investigator who has already been trained by the supporting company's designated personnel.
- The curriculum vitae and any relevant qualifications of the individual have been reviewed and approved by the Inovio or its designee to perform the procedure.

Any deviation from the above procedures must be approved by Inovio and MDACC IND Office or its designee.

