1.6. Study Design

This study will be an open label, multi-cohort, phase II trial for the combination therapy of MEDI0457 (INO-3112) and Durvalumab (MEDI4736) in patients with HPV-16 and/or -18 related malignancies. This study will enroll 3 cohorts of patients with HPV-16/18 (+) tumors. The three cohorts are:

- 1. HPV-16/18 cervical cancer,
- 2. HPV-16/18 rare tumors (anal, penile, vulvar, vaginal), and
- 3. HIV (+) HPV-16/18 malignancies (any site).

Each cohort will have a two-stage design with predetermined stopping rules based on ORR after stage I and each cohort will function independently clinically. After each cohort completes accrual to stage I, only the two cohorts with the most responses will move on to stage 2.

Therefore, accrual to stage 2 will not start till all three cohorts have completed stage I. However, if a single cohort has a high response rate (≥4 responses out of 9 patients), the second stage of accrual may proceed prior to other cohorts completing stage I.

At the onset of the study, only patients with cervical, vulvar, or vaginal cancers will be enrolled for the first 3 slots. Once all 3 of these patients have completed the first 6 weeks of treatment, enrollment will be opened to all included cancer histotypes.

Both MEDI0457 and durvalumab treatment will continue until confirmed disease progression or unacceptable toxicity. Either treatment may be stopped by the investigator if a SAE is deemed to be related to that treatment while the other treatment continues.

The target population consists of male or female patients 18 years of age or older with recurrent or metastatic HPV 16- or 18-associated cancers with persistent or progressive disease (PD) after initial standard-of-care treatment and lacking a curative treatment option.

Eligible patients must have at least one "measurable target lesion"—according to RECIST version 1.1—that has not been previously irradiated. In addition, if the primary lesion is not large enough for a biopsy without changing radiologic findings for following response, one additional lesion

Version Number: 1.8 Date: July 26, 2019

Proprietary of MD Anderson Cancer Center

that can be safely biopsied at screening and prior to the first dose of MEDI0457 at Week 1 will be required.

All patients will receive combination treatment with MEDI0457 and durvalumab as per the **Planned Dosing Schedule (Section 4.4.1, Figure 1**, and **Table 3**).

[figure not shown]

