3.4. Discontinuation of Investigational Product

An individual patient will not receive any further IP if any of the following occur.

- Initiation of subsequent anticancer therapy including another investigational agent.
- Confirmed PD: the initial assessment of PD by RECIST v1.1 (baseline PD assessment) will be confirmed by a repeat evaluation at the next tumor assessment time point, but no sooner than 4 weeks later. If any tumor assessment time point (beyond the first PD assessment) shows ≥ 20% increase in the overall tumor burden (the sum of diameters of target lesions and new lesions), when compared to the baseline PD assessment (the sum of diameters of target lesions and new lesions), the patient would be deemed as having confirmed PD and must be discontinued.
- An AE that, in the opinion of the Investigator, supporting company, or the MDACC IND Office, contraindicates further dosing.
- Patient experienced a DLT as defined in Section 6.7.2.
- Withdrawal of consent from further treatment with IP or lost to follow-up.

Version Number: 1.8 Date: July 26, 2019

Proprietary of MD Anderson Cancer Center

- Patient is determined to have met one or more of the exclusion criteria or failed to meet all of the inclusion criteria for study participation and continuing to receive IP might constitute a safety risk.
- Pregnancy or intent to become pregnant.
- Non-compliance with the study protocol that, in the opinion of the Investigator, supporting company, or the MDACC IND Office, warrants withdrawal from treatment with IP (e.g., refusal to adhere to scheduled visits).
- The treating Physician determines it is not in the best interest of the patient to continue.

At any time, patients are free to discontinue IP or withdraw from the study (i.e., IP and assessments) without prejudice to further treatment. If a patient is withdrawn from study, see Section 3.5.2.

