5. STUDY PLAN

All study procedures will be performed according to **Table 3**.

Version Number: 1.8 Date: July 26, 2019

Proprietary of MD Anderson Cancer Center

Table 3. Schedule of Study Procedures

	Screening	(Cycle 1		Cyc	ele 2	Cy	cle 3	Cycle 4 ^a	Cycle 5 ^a	EOT ^b	Follow-up ^c
Week of Study	-	1	3	4	7	8	10	12	16	20	-	-
Procedures Day of Week	-28 to -1	1 ±7 days (unless otherwise noted)										
Informed consent	X											
Demographics	X											
Medical histories ^d	X											
Inclusion/exclusion criteria	X	X										
Physical examination ^e	X	Xf	X	X	X	X	X	X	X	X	X	
ECOG performance status	X	X^{f}	X	X	X	X	X	X	X	X	X	
Adverse events assessment	X	X	X	X	X	X	X	X	X	X	X	
Concomitant medications/procedures	X	X	X	X	X	X	X	X	X	X	X	
Disease status ^g	X ^h							Xi		X ^{i,j}	X	X^k
Hepatitis/HIV screening ¹	X											
Vital signs ^m	Xg	Xf	X	X	X	X	X	X	X	X	X	
12-lead ECG	X	Xf				X		X		X ⁿ	X	
HPV typing ^o	X											
Hematology ^p	X	Xf	X	X	X	X	X	X	X	X^q	X	
Serum chemistry ^r	X	Xf	X	X	X	X	X	X	X	X^q	X	
Coagulation testing ^s	X	As clinically indicated.										
Thyroid function testing ^t	X	X^{f}		X		X		X	X	X^q	X	
Urinalysis ^u	X	As clinically indicated.										
Pregnancy test ^v	X^{w}	X ^x		X		X		X	X	X	X	
MEDI0457 administration ^y		X	X		X			X		X		
MEDI0457 post-treatment reaction ^z		X	X		X			X		X		
Download EP data		X	X		X			X		X		
Durvalumab administration ^{aa}				X		X		X	X	X		
Tumor biopsy ^{bb}	X						Xcc				X^{dd}	
Immune Profiling/HPV Serology Research Bloodee		X		X		X	X		$X^{\rm ff}$		X	
Pharmacokinetics/ADA Research Blood ^{gg}				X		X			X^{hh}			
Viral load ⁱⁱ	X			X		X		X	X	X	X	
HBV DNA/Hep BsAg ^{jj}				X		X		X			X	

Version Number: 1.8

Proprietary of MD Anderson Cancer Center Date: July 26, 2019

- ^a Patients can continue on the study until progression or unacceptable toxicity as long as the physician feels the patient is receiving benefit. Cycles 4 and 5 should be repeated to continue this treatment. ^b End of treatment (EOT) is defined as the last visit where the decision is made to discontinue protocol directed treatment.
- ^c A clinic visit is not required for follow-up. Patients who are taken off study due to disease progression or intolerable toxicities will be followed for vital status every 6 months via phone and/or review of medical record.
- ^d Histories include medical history, history of prior cancer treatment, history of procedures

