- ^e Complete physical examination during Screening and at the Follow-up visit; targeted physical examination at all other visits.
- f If performed within 3 days prior to Day 1, they do not need to be repeated.
- g The preferred method of disease assessment is CT with contrast. The same method is preferred for all subsequent tumor assessments for the same patient. Patients discontinued from treatment for reasons other than PD will continue disease assessments until confirmed PD or start of subsequent anticancer therapy.
- h Magnetic resonance imaging scan of the brain will be performed only at screening or at each assessment if the patient is neurologically symptomatic during treatment outside of the setting where the patient has known central nervous system metastases.
- ¹ If possible, disease status assessments will be performed on the day prior to scheduled drug administration.
- ^j Disease status assessments will be performed every 8 weeks (± 3 days) (relative to the date of the first MEDI0457 administration) for 1 year, if CR/PR/SD are achieved then disease status assessments should be performed every 12 weeks (± 7 days) until the EOT.
- k If no PD, disease assessment should be performed on Day 90 (± 7 days) after EOT, every 3 months (± 7 days) after Day 90 up to Month 12, and then every 6 months (± 14 days) after Month 12 until the end of study (EOS).
- ¹ Hepatitis screening tests include: HBV-DNA, HCV-Ab, HBsAg, HBcAB, and HBsAb.
- Temperature, respiratory rate, pulse oximetry, blood pressure, HR and weight. Height will be measured only during Screening. See Section 6.5.7 for details.
- ⁿ Every 12 weeks until end of treatment.
- o Historical tissue samples may be used; there is no need for additional samples/test for the HPV 16/18 test to be collected just for this protocol.
- P Hematology panel includes: basophils, eosinophils, hematocrit, hemoglobin, lymphocytes, mean corpuscular hemoglobin, mean corpuscular hemoglobin, concentration, mean corpuscular volume, monocytes, neutrophils, platelet count, red blood cell count, total white cell count. For patients in the HIV(+) cohort, CD4 and CD8 counts will be performed.
- ^q Every 4 weeks for first 12 months and every 3 months thereafter until study discharge.

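### Section 4.4.2 caps durvalumab at 13 doses while 1.6, 4.4.1 and Table 3 continue it without a cap, so the instructions conflict from Week 56

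*Combined protocol and SAP*

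**What the plan says.** All references are to the combined protocol and SAP.

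- **Cap (4.4.2, Durvalumab):** "The maximum number of doses of checkpoint inhibitor therapy will equal 13".
- **Schedule (4.4.1):** "Durvalumab will be administered on Week 4, Week 8, Week 12 and then every 4 weeks until disease progression or unacceptable toxicity".
- **Design (1.6):** "Both MEDI0457 and durvalumab treatment will continue until confirmed disease progression or unacceptable toxicity".
- **Table 3, footnote a:** "Patients can continue on the study until progression or unacceptable toxicity as long as the physician feels the patient is receiving benefit", followed by "Cycles 4 and 5 should be repeated to continue this treatment". Cycles 4 and 5 are Weeks 16 and 20, and both columns are marked for durvalumab.
- **Discontinuation (3.4)** opens with "An individual patient will not receive any further IP if any of the following occur". Reaching a maximum number of doses is not among the events that follow.
- **MEDI0457 (4.4.1)** is given at Weeks 1, 3 and 7, then "Week 12 and then every 8 weeks until disease progression or unacceptable toxicity". Section 6.7.1 lets the investigator stop either drug while the other goes on.
- **End of treatment (EOT)** is defined in Table 3 footnote b as the visit at which the decision to stop protocol treatment is made. After the first year, footnote j says "disease status assessments should be performed every 12 weeks (± 7 days) until the EOT".

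**The concern.** One sentence sets a ceiling on durvalumab. Three other places give an open-ended schedule, and none of them mentions the ceiling. A patient who reaches the ceiling without progression or unacceptable toxicity is therefore covered by two opposite instructions.

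What is at stake is the durvalumab actually given after about one year, and the dates that run from its last dose. Section 3.3.1.2 counts 90 days from the last durvalumab dose for certain concomitant drugs. Sections 3.5 and 7.4.1 count 90 days of follow-up and adverse event recording from the last dose of durvalumab and/or MEDI0457. Patients treated this long also supply the later part of the PFS and OS curves, so a description of the regimen behind those curves should not depend on which paragraph was read.

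**Working it through.** **1. The plan's figure.** The protocol gives no derivation for 13 doses, so there is nothing to reproduce. It can only be placed on the calendar.

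**2. Durvalumab calendar (4.4.1).** Doses at Weeks 4, 8, 12 and every 4 weeks after that put dose k at Week 4k.

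| Dose k | Week 4k | 4.4.2 | 1.6, 4.4.1, Table 3 footnote a |
|---|---|---|---|
| 13 | 52 | last dose allowed | give |
| 14 | 56 | not allowed | give |
| 19 | 76 | not allowed | give |
| 26 | 104 | not allowed | give |

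A patient treated for two years would receive 26 doses under one reading and 13 under the other.

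**3. Skipped doses.** With s skipped doses, dose 13 falls at Week 4 × (13 + s): Week 56, 60 or 64 for s = 1, 2 or 3. The conflict starts at the next scheduled dose, 4 weeks later. Week 52 is thus the earliest date for dose 13 and Week 56 the earliest for the conflict.

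**4. MEDI0457 calendar (4.4.1).** Weeks 1, 3, 7, 12, 20, 28, 36, 44 and 52 make 9 doses; Weeks 60, 68 and so on follow, with no cap. The direct conflict concerns durvalumab only. For MEDI0457 the text is silent on what follows dose 13.

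**5. How many patients.** The documents give no expected PFS, so this step is an assumption: exponential PFS with a median of 4 to 6 months, and 12 months taken as the approximate time of the cap.

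- Median 4 months: 0.5^(12/4) = 0.125.
- Median 6 months: 0.5^(12/6) = 0.25.

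| Enrolment (8.1.1) | n | × 0.125 | × 0.25 |
|---|---|---|---|
| All cohorts stop after stage 1 | 3 × 9 = 27 | 3.4 | 6.8 |
| One cohort completes stage 2 | 34 + 2 × 9 = 52 | 6.5 | 13.0 |
| Maximum | 2 × 34 + 9 = 77 | 9.6 | 19.3 |

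These are counts of progression-free patients, not of patients on drug. Stops for toxicity or withdrawal lower the number on treatment, and skipped doses delay dose 13. Treatment beyond confirmed progression (6.3) raises the number.

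**6. Primary design.** The rule in 8.1.1 counts responders (at least 2 of 9, then at least 9 of 34) and does not use treatment duration. Its rejection probability is the sum over x = 2 to 9 of P(Bin(9, p) = x) × P(Bin(25, p) ≥ 9 − x). This gives 0.047 at p = 0.15 and 0.811 at p = 0.35, in line with the stated 0.05 and 80%. Nothing here changes with the cap.

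**The case against.** The strongest reply is that both rules can be obeyed at once: stop at progression, at toxicity or at 13 doses, whichever comes first. The cap is a specific sentence in the durvalumab section, and footnote a is partly permissive. That reading is possible, but no passage states it. Sections 1.6 and 4.4.1 are unqualified, footnote a directs that cycles containing durvalumab be repeated, and 3.4 omits the cap. The cap's own paragraph also refers to a monotherapy arm, which this trial does not have, so its text cannot simply be presumed to govern.

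The other objections limit the consequences, and they largely stand:

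- **A reader might infer that EOT and the safety window are undefined.** They are not. Footnote b defines EOT, and the 90-day window runs from actual last doses.
- **A reader might infer that MEDI0457 has no rule after dose 13.** Sections 4.4.1 and 6.7.1 point to its continuing; what is missing is an express statement.
- **A reader might infer a marked change in scan timing.** After year 1, on-treatment scans are every 12 weeks (84 days). After EOT without progression the first is at Day 90, then every 3 months up to Month 12 (footnote k). Just before and after EOT these are nearly the same. The text does not say where Month 12 is counted from, so later divergence cannot be sized.
- **A reader might infer that practice will differ between sites.** The protocol does not establish several enrolling sites. Differences between investigators are the most that can be said.
- **Endpoints.** PFS and OS are secondary and single-arm, with no planned one-year landmark, and 8.3.1 counts RECIST assessments whether or not treatment has stopped.

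**Conclusion.** The inconsistency is real and worth correcting. From Week 56, or later if doses were skipped, 4.4.2 forbids a durvalumab dose that 1.6, 4.4.1 and Table 3 footnote a call for. The effect is on late durvalumab exposure and on dates tied to the last durvalumab dose. It does not reach the primary ORR analysis or the Simon design.

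The number of patients is not known. The range of about 3 to 7 of 27 up to about 10 to 19 of 77 rests on an assumed exponential PFS with a median of 4 to 6 months. The upper end also needs maximum enrolment, so it should not be read as an expected count. No view is taken on which duration is right.

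**What to change.** Reconcile 1.6, 3.4, 4.4.1, 4.4.2 and Table 3 footnote a so that a single durvalumab duration appears in all five. State whether MEDI0457 continues after the last durvalumab dose, so that the existing EOT definition applies without doubt. No new EOT definition is needed. The choice of duration belongs to the sponsor and the investigators.

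The change is to wording only, with no effect on sample size or analysis. It is still a protocol amendment, and 9.4 requires approval by the IRB and the supporting company before it is implemented.
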